5.2.5 Dosing schedule/treatment schedule, maintenance therapy (Part A and Part B)

For all patients completing induction therapy in Parts A and B, and who are deriving clinical benefit at Week 8 (as defined in Section 10.2), maintenance therapy may be given. A patient's maintenance therapy will be the same as their induction therapy and will be given every eight weeks for up to one year after their first BI-1206 dose on the study (Week 1 of induction therapy).

- For patients in Arm 1 in Parts A and B (single agent arms) who continue on maintenance therapy, the dose of BI-1206 will be continued at the level of the last dose received in their induction therapy.
- For those patients in Arm 2 in Parts A and B (combination arms) who continue on maintenance therapy, these patients will continue to receive BI-1206 and rituximab at the level of the last dose received in their induction therapy.

5.3 Communication Plan where dose escalation (Part A) is to occur

5.3.1 Organisation and preparation for dose decision meetings.

Dose decision meetings will be organised by the Sponsor for weekly review of patient data during the first three weeks of the intra-patient dose escalation cohort in Arm 1 only, and subsequently during or following Week 5 of the last patient recruited to each cohort in Arm 1 or in Arm 2. Dose decision meetings will be triggered and occur independently for each treatment arm.

Required attendees/functional groups are as defined in the Sponsor's SOP: Sponsor Pharmacovigilance (PV) representative, Sponsor Medical Sciences representative (MS), Sponsor Clinical Study Manager or appropriate delegate, CI and PIs with patients at their sites undergoing review (a nominated sub- or co-investigator may attend in the PI's place if necessary). Optional attendees are Research Nurses or other relevant site staff and the following Sponsor representatives; Clinical Research Associates (CRAs), Clinical Study Co-ordinator (CSC), Clinical Data Manager (CDM) and, Project Leader (PL). PI's who do not have patients in the cohort under review are encouraged to attend but not required.

Prior to the dose decision meeting, the Sponsor will distribute the agenda and all necessary data to the meeting attendees and all study PIs if they are not available to attend the meeting, specifying which patients and data will form part of the review. The essential data to be reviewed to make decisions concerning changes in dose will be defined in the monitoring guidelines for the study. These will consist primarily of clinical data listings from Data Management (DM), safety data listings from PV and available pharmacokinetic and pharmacodynamic (PK/PD) assay data.

For intra-patient dose escalation, in order to ensure that the most recent trial data is under review data listings will be reviewed alongside anonymised safety data signed off by the site Investigator and faxed or emailed from site directly.

The dose decision for treatment of subsequent patients will be based upon safety data from all patients in a cohort after the last patient in the existing cohort completes their induction therapy and has been followed up for a minimum of 7 days following their fourth dose. Data from any previous cohorts in the same arm and data from complete/incomplete cohorts in the other arm will also be taken into account in dose decision meetings. Any available data from any other trials investigating BI-1206 will also be considered in the dose decision meetings.

5.3.2 Areas to be discussed at dose decision meetings.

Areas which should be discussed at the dose decision meeting include:

- Outline any relevant criteria specified by the protocol relating to changes in dose levels to the attendees e.g. study dose escalation scheme, dose limiting toxicity (DLT) criteria, criteria for expansion of cohorts (including any \geq Grade 2 related toxicity considered to be clinically relevant as defined in Section 5.4.2) etc. Patients treated since the last dose review meeting including IMP related adverse events noted and duration of treatment.

- Assessment and agreement on any dose limiting toxicities that may have occurred and resulting actions.
- Relevant PK and/or PD data available since the last dose decision meeting and any proposals to amend PK/PD scheduling based on emerging data (Section 8). In event of any changes to the sampling schedule, it should be noted the total blood volume and burden of the patient will not increase.
- Any available data from any other trials investigating BI-1206.
- Any additional relevant information relating to adverse events or patient safety which may have arisen following distribution of listings for the meeting and will therefore not be documented in the listings.
- Any possible concern after the review of cumulative data.
- Assessment and agreement on the appropriate next dose level or other action such as dose expansion, dose reduction or halt to recruitment.
- If the next cohort should be a minimum of one patient cohort or 3+3 cohort based on the emerging safety data.
- If it is appropriate to open the combination arm (Arm 2) and agreement of starting dose and size of cohort for the first cohort based on available data from Arm 1.

5.3.3 Follow-up of dose decision meetings

Following the meeting the Sponsor will prepare and disseminate minutes documenting the data reviewed per patient and any outcomes or decisions made. Dose limiting toxicities, SAEs, medically important events (as specified by the protocol) and suspected unexpected serious adverse reactions (SUSARs) discussed will be documented in the minutes and listed by patient. If changes to these emerge as part of the review and discussion the minutes will reflect these and any actions to be taken as a result. Dose decision meeting minutes will be distributed by the Sponsor to the CI, all study PIs and any other relevant site staff.

If due to exceptional circumstances, the CI is not able to attend the dose review meeting, the meeting minutes will be sent to the CI by email who will respond to confirm agreement with the dose decision and cohort size prior to recruitment of the next patient to the relevant cohort.

The outcome of the dose review will also be approved by the Sponsor's Head of Medical Sciences before recruitment of the next patient to the relevant cohort. Patients can only be registered and treated on the study following email confirmation from the Sponsor to the site of the agreed dose level and assigned treatment arm (single agent or combination) for the specific patient.

5.3.4 Dissemination of Safety data between dose decision meetings

Safety information relating to SUSARs will be collected and provided to the MHRA and Ethics Committee as outlined in Section 9. Where the Sponsor becomes aware of significant relevant safety information (such as a DLT or clinically relevant \geq Grade 2 related toxicity to expand a cohort from a minimum of one patient to 3+3 cohorts) during treatment of patients on the study, this will be communicated to all PIs and relevant site staff by email as soon as is reasonably possible. Updates regarding the DLT assessment and actions to be taken will also be provided by email where needed with follow-up phone-calls where required.

5.4 BI-1206 single agent dose escalation scheme (Part A, Arm 1)

The weekly doses to be administered to each cohort are shown below (Table 1). Intermediate doses may be examined, e.g. a dose between 400 mg and 800 mg could be chosen for further investigation based on a review of the emerging safety data but in any event, dose increases will not exceed those described below. Intermediate dose levels will only be explored if deemed clinically appropriate after review of a completed cohort in Arm 1 and agreed in a dose decision meeting (see Section 5.3). The maximum weekly dose to be administered will be 800 mg.

An accelerated dose escalation scheme will be used in the initial dose levels which will occur in a minimum of one patient. Intra-patient dose escalation will be permitted until either a DLT is reported or the dose reaches 100 mg, which is above the expected PAD determined based on the preclinical toxicology data (>60 mg).

Please refer to Section 5.3 for details of the communication plan and process for dose escalation review and dissemination of information. In Cohort 1, if a patient withdraws before completing induction therapy for reasons other than DLT they will be replaced, following a dose review meeting with the Sponsor and CI at which the planned dose level for the replacement patient will be decided. The replacement patient would start treatment at a dose level that the previous patient has already received and the dose level at subsequent weeks would increase to a maximum of 50 mg in line with the dose escalations described in Table 1, so they may receive a dose of 50 mg for more than one week.

The decision to dose escalate between cohorts will be based on the four weeks (one week after the Induction Therapy Week 4 dose) safety data from patients in the current cohort and all available safety data from previous cohorts.

Table 1: Proposed single agent dose escalation schedule (subject to revision based upon emerging safety data; Part A, Arm 1)

Cohort Number	Total BI-1206 Dose (mg)	Cohort size ^b	Notes
1 (pt1 wk 1)	0.4		
1 (pt1 wk 2)	2		
1 (pt1 wk 3)	10	1	
1 (pt1 wk 4)	50		
Assess patient for safety for 7 days post Week 4 infusion before next cohort or before each patient if Cohort 1 consists of more than one patient			
Follow the last patient for safety in each cohort to 7 days post Week 4 infusion before the next cohort is opened to recruitment (all cohorts going forward)			
2	100	1 ^a - 3	
3	200	1 ^a - 3	
4	400	1 ^a - 3	
5	800	3 + 3	

^a Assumes that no clinically relevant ≥Grade 2 related toxicity has occurred

^b Assumes that no DLTs are encountered and is also dependant on number of patients that need to be replaced (if patient withdraws for reasons other than DLT).

5.4.1 Action if DLT observed in Cohort 1 (0.4mg to 50 mg), Part A Arm 1

Cohort 1 will consist of a minimum of a single patient, with intra patient dose escalation permitted up to a maximum weekly dose of 50 mg. Safety data will be reviewed on a weekly basis prior to the next planned dose and a decision to dose-escalate will be made based on this data.

If a DLT is observed at or below a dose of 50 mg the cohort will be expanded to up to six patients at the dose level at which the DLT is first identified (the most recent dose prior to onset of the event identified as a DLT). If one out of the six patients experiences DLT, intra-patient dose escalation will cease but standard dose escalation will continue; subsequent cohorts will be expanded to three patients. If two or more out of the six patients experiences a DLT, decisions about future patients will be made in accordance with Figure 4.

5.4.2 Dose escalation and action if clinically relevant \geq Grade 2 related toxicity observed at dose levels from Cohort 2 onwards, Part A Arm 1

From Cohort 2 onwards, all cohorts will include a minimum of one patient (see Figure 4)

- In the first patient recruited, any episode of clinically relevant \geq Grade 2 related toxicity would trigger cohort expansion to a minimum of 3 patients.
- Clinical relevance of the related toxicity will be determined by review and agreement between the relevant Investigator, Chief Investigator and Sponsor according to the following definition:

[figure not shown]
The test of clinical relevance is that the adverse event in question would cause the Investigator to re-evaluate the risk-benefit assessment of continuing therapy for the patient experiencing the event and to conclude that on a balance of probabilities, the risk-benefit ratio could be materially worsening

- The decision to expand a minimum of one patient cohort to a 3+3 cohort following a clinically relevant \geq Grade 2 related toxicity will be documented and distributed by the Sponsor to all Investigators as per Section 5.3.4. The decision may occur outside the dose decision meetings as it is dependent on when the event/s occurs. The assessment of a clinically relevant toxicity will end at Week 5 (same as the DLT period i.e. one week post fourth infusion).
- As per Section 9.4, related toxicity will be highly probably, probably and possibly related to BI-1206 (or rituximab in Arm 2).

It should be noted that dose escalation and cohort size decisions will be made based on data from completed cohorts in the single agent arm (Arm 1); available data from the combination arm (Arm 2) will be also be reviewed and considered in the Arm 1 dose decision meetings. Please refer to Section 5.3 for details of the communication plan, the process for dose escalation review and decision making and the dissemination of information.

All patients in a cohort must have completed induction therapy and 7 days post the fourth infusion for dose-escalation to the next cohort to occur. The second patient in any cohort will not commence treatment until after the first patient in that cohort has completed two infusions of BI-1206; the third patient in any cohort will not commence treatment until after the second patient in that cohort has completed one infusion of BI-1206.

Figure 4: Dose escalation decision-making and action if clinically relevant \geq Grade 2 related toxicity and/ or DLT observed at dose levels from Cohort 2 (Part A, Arm 1)

dx = initial dose level dx +1 = 1 level above initial dose

5.4.3 Dose escalation and action if a DLT observed at dose levels from Cohort 2 onwards, Part A, Arm 1

If one instance of DLT is observed in any cohort, the cohort will be expanded to include up to six patients. If one out of the six patients experience a DLT then dose escalation will continue, and the next cohort will consist of a minimum of 3 patients as described in Figure 4. If no DLTs are seen in 3 patients, further escalations will continue as 3+3 cohorts.

No additional patients will be added to a cohort after a second DLT is observed. Should DLT occur in more than two out of three or two out of six patients in a cohort, the previous dose level may not be the most appropriate RP2D. Intermediate dose levels may be explored if deemed clinically appropriate after review of a completed cohort, see Section 3.4.

Please refer to Section 5.3 for details of the communication plan and process for dose escalation review and dissemination of information. The proposed dose escalation scheme in Table 1 may be modified in light of emerging safety data following consultation between the Sponsor and the CI.

5.5 BI-1206 and rituximab escalation cohorts (Part A, Arm 2)

The combination escalation arm (Part A, Arm 2) will open to recruitment following review of a completed single agent dose level in Arm 1. The starting dose for BI-1206 in combination with rituximab will be agreed at a dose decision meeting based on data from completed cohorts in the single agent arm. The combination dose will not exceed the highest dose of BI-1206 safely given (≤ 1 DLT in up to six patients) as a single agent to date and must be deemed clinically appropriate to combine with rituximab.

The dose(s) of rituximab will be 375 mg/m² based upon the approved dose of rituximab. For the purpose of this trial, all patients including CLL patients will receive 375 mg/m² for every rituximab infusion for consistency.

Once the combination escalation arm (Part A, Arm 2) is opened, it will run in parallel to the single agent escalation arm (Part A, Arm1) but dose decisions and cohort size decisions will be made independently for each arm. Combination cohorts will also be a minimum of one patient and dose escalation/cohort expansion decision-making as described in Sections 5.4.2 and 5.4.3 will also apply to the combination escalation cohorts.

It should be noted that dose escalation decisions will be based on data from the combination arm (Arm 2) with available data from the single agent arm (Arm 1) and any other ongoing trials with BI-1206 also being reviewed and considered. Please refer to Section 5.3 for details of the communication plan and process for dose escalation review and dissemination of information.

All patients in a cohort must have completed induction therapy and 7 days post the fourth infusion without DLT for dose-escalation to the next cohort to occur. The second patient in any cohort will not commence treatment until after the first patient in that cohort has completed two infusions of BI-1206 in combination with rituximab; the third patient in any cohort will not commence treatment until after the second patient in that cohort has completed one infusion of BI-1206 and rituximab.

In Part A, Arm 2 the dose level of rituximab will be fixed and the dose level of BI-1206 will be explored in the escalation phase in order to establish the BI-1206 MAD or MTD and RP2D in combination with rituximab, see Section 3.4.

The BI-1206 doses explored in Part A, Arm 2 may follow the dose levels outlined in Table 1 but will be dependent on emerging data. Intermediate BI-1206 doses may be examined, e.g. a dose between 400 mg and 800 mg could be chosen for further investigation based on a review of the emerging safety data but in any event, dose increases will not exceed those described in Table 1. Intermediate dose levels will only be explored if deemed clinically appropriate after review of a completed cohort in Arm 2 and agreed in dose decision meeting (see [Section 5.3](#)).

The maximum weekly BI-1206 dose to be administered will be 800 mg in both Arm 1 and Arm 2.

5.6 Cohort expansion at maximum tolerated and/or maximum administered dose (Part A, Arm 1 and Arm 2)

Cohorts may be expanded to six patients as described in Sections 5.4.1 and 5.4.2. If only one out of six patients experiences a DLT, dose escalation will continue. If two out of up to six (i.e. between two and six) patients experience a DLT dose escalation will stop and this dose will be defined as the maximum administered dose (MAD). At least six patients will be treated at a dose below the MAD to define the MTD.

The MAD could also equal the MTD in the event that dose escalation is stopped before two DLTs are observed at a given dose level due to the expectation that higher dose levels would be too toxic to administer to patients, or if the 800 mg dose level is reached.

The single agent RP2D in Part B, Arm 1 of the proposed clinical trial will be determined by the Sponsor, CI and PIs, following review of all available PK/PD and clinically relevant toxicity data for all patients entered onto the trial in Part A (Arm 1 and Arm 2), and the identified MTD or MAD.

The combination RP2D in Part B, Arm 2 of the proposed clinical trial will be determined by the Sponsor, CI and PIs, following review of all available PK/PD and clinically relevant toxicity data for all patients entered onto the trial in Part A (Arm 1 and Arm 2), and the identified MTD or MAD.

Any available data from other trials investigating BI-1206 will also be considered in defining the RP2D in Arm 1 and Arm 2. The RP2D for each arm may be the same or different but it will not exceed 800 mg as per Table 1.

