3.4 Definition of maximum tolerated dose

3.4.1 Part A, Arm 1:Single-agent dose escalation

If two out of up to six patients at the same dose level experience a DLT as defined in Section 3.3, this dose level of BI-1206 will be considered the maximum administered dose level (MAD) and no further patients will be treated at this dose level. In this case, the maximum tolerated dose (MTD) will be determined as a dose level below the MAD, which could be a dose previously administered or an intermediate dose between a dose already administered and the MAD. This MTD will be agreed following the review of all the relevant toxicity data between the Sponsor and the study team, including the Chief Investigator.

The MAD could also equal the MTD in the event that dose escalation is stopped before two DLTs are observed at a given dose level due to the expectation that higher dose levels would be too toxic to administer to patients, or if the 800 mg dose level is reached.

The RP2D in Part A, Arm 1 which will be used in Part B, Arm 1 of the clinical trial, will be determined by the Sponsor, Chief Investigator and Principal Investigators, following review of all relevant pharmacokinetic/pharmacodynamic (PK/PD) and clinically relevant toxicity data for all patients entered onto the trial in Part A Arm 1, and the identified MTD or MAD. All significant toxicities and available data from Part A, Arm 2 and data from any other trials investigating BI-1206 will also be considered in the determination of the RP2D.

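### For an Arm 2 cohort below 800 mg with one DLT in six patients, Section 5.5 bars escalation while Sections 5.4.3 and 5.6 say it continues

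*Combined protocol and SAP*

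**What the plan says.** Four places in the protocol govern escalation in the combination arm when a DLT has occurred.

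- **Section 5.5, escalation condition.** Every patient in the cohort must have "completed induction therapy and 7 days post the fourth infusion without DLT for dose-escalation to the next cohort to occur".
- **Section 5.5, import of the Arm 1 rules.** Decision-making "as described in Sections 5.4.2 and 5.4.3 will also apply to the combination escalation cohorts". The section adds: "Combination cohorts will also be a minimum of one patient".
- **Section 5.4.3, imported by 5.5.** A first DLT enlarges the cohort, to six at most. The rule for the result is: "If one out of the six patients experience a DLT then dose escalation will continue". On the size of the cohort that follows such a result, Section 5.4.3 states that "the next cohort will consist of a minimum of 3 patients".
- **Section 5.6, headed for Arm 1 and Arm 2.** "If only one out of six patients experiences a DLT, dose escalation will continue". Escalation stops at two DLTs.

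The Arm 1 counterpart of the 5.5 condition is in Section 5.4.2. It requires that all patients have "completed induction therapy and 7 days post the fourth infusion for dose-escalation to the next cohort to occur". It matches the 5.5 sentence except that it does not require freedom from DLT.

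The MAD is defined in Section 3.4.1, which 3.4.2 adopts for Arm 2. Its trigger reads: "If two out of up to six patients at the same dose level experience a DLT". Primary endpoint (c) seeks the highest dose, up to 800 mg, at which no more than one of up to six patients has a related DLT.

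**The concern.** The rules agree when a cohort has no DLT and when it has two or more. They disagree for exactly one DLT in six, which is the borderline result that expansion to six exists to resolve. Read literally, the 5.5 sentence means that expanding an Arm 2 cohort after a first DLT could never lead to escalation, because the condition has already failed.

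Two things follow for the primary objective. First, whether the next dose level is tested can change which dose becomes the combination MTD. Second, if escalation stops under 5.5 after a single DLT, the two-DLT trigger for the MAD has not been met. Section 3.4.2 names two circumstances in which the MAD may equal the MTD without two DLTs: higher doses are expected to be too toxic, or 800 mg has been reached. Section 5.5 states neither.

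The MTD or MAD is considered with PK/PD, toxicity and other-trial data when the RP2D is set, and that dose is given to up to 25 patients in Part B Arm 2.

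**Working it through.** **The contradiction, by outcome (Arm 2 cohort below 800 mg)**

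| Outcome | 5.5 sentence | 5.4.3 and 5.6 |
|---|---|---|
| No DLT | escalation possible | escalation possible |
| One DLT in six | no escalation | escalation continues |
| Two or more DLTs | no escalation | no escalation |

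The limit to cohorts below 800 mg is needed because no higher dose is allowed. Section 3.5.4 counts a patient with a DLT as evaluable for Arm 2 escalation decisions, so the middle row cannot be set aside as unevaluable. This part needs no numbers. It does not depend on Figure 4 either, since the one-in-six rule is stated in words.

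**How often the rules would part**

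The documents state no DLT rate and no operating characteristics, so there is no planned figure to reproduce. Let *p* be the DLT rate at a dose level (an assumption) and *n* the number of patients treated before expansion. Section 5.5 allows *n* = 1; Section 5.4.3 sets at least three for the cohort after a one-in-six result. Patients are taken as independent, and expansion for Grade 2 toxicity is ignored at first.

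- 5.5 wording: P(escalate) = (1 − p)^n
- 5.4.3/5.6 wording: P(escalate) = (1 − p)^n + n·p·(1 − p)^5
- Gap = P(exactly one DLT in six, the DLT among the first n) = n·p·(1 − p)^5

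For p = 0.10, (0.9)^5 = 0.590:
- n = 1: 0.900 against 0.900 + 0.059 = 0.959
- n = 3: 0.729 against 0.729 + 0.177 = 0.906

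For p = 0.20, (0.8)^5 = 0.328:
- n = 1: 0.800 against 0.800 + 0.066 = 0.866
- n = 3: 0.512 against 0.512 + 0.197 = 0.709

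Over a wider range for the three-patient start:
- p = 0.05: 0.857 against 0.973 (gap 0.116)
- p = 0.30: 0.343 against 0.494 (gap 0.151)

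**Upper bound.** The derivative of p(1 − p)^5 is (1 − p)^4·(1 − 6p), which is zero at p = 1/6. There (1/6)(5/6)^5 = 0.067, so the gap cannot exceed 6.7 points for n = 1 or 3 × 6.7 = 20.1 points for n = 3, whatever the true rate.

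**Once a first DLT has triggered expansion.** Given exactly one DLT among the first n, the chance of ending in the disputed state is (1 − p)^(6 − n):
- n = 1: 0.9^5 = 0.590 at 10%; 0.8^5 = 0.328 at 20%
- n = 3: 0.9^3 = 0.729 at 10%; 0.8^3 = 0.512 at 20%

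**Effect of Grade 2 expansion.** Suppose a one-patient cohort whose first patient has no DLT is enlarged to three with probability g. The gap becomes p(1 − p)^5 + (1 − p)·g·2p(1 − p)·(1 − p)^3 = (1 + 2g)·p(1 − p)^5. This lies between the one-patient and three-patient figures.

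**The case against.** The best case against is that the intended rule can be recovered. Section 5.5 expressly imports 5.4.3, Section 5.6 repeats the one-in-six rule for both arms, and 3.4.1, 3.4.2 and endpoint (c) all use the two-DLT threshold. Only two words in 5.5 stand against this. The sentence also opens a paragraph about timing and staggering, so it could be read as the default condition, with 5.4.3 taking over once a DLT occurs. The Arm 1 sentence supports that reading. It too requires all patients to have completed induction, yet under 5.9.5 and 5.9.9 a patient with a DLT may stop early and is not replaced. Taken literally, it would then also block escalation, which 5.4.3 clearly does not intend.

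This reading is plausible, but no text states it. The 5.5 sentence covers every patient in the cohort, makes no exception for expanded cohorts, and adds a condition that its Arm 1 counterpart lacks. A reader cannot tell a deliberate stricter rule for the combination from a slip.

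A second argument is that dose decision meetings agree each step and that the Sponsor must approve it (5.3.2, 5.3.3). That lowers the risk of unconsidered action. But those meetings are told to work from the protocol's criteria, and here the criteria conflict.

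Two smaller points stand in part. Section 3.4.2 is permissive about when the MAD may equal the MTD, although it gives no route other than the two named. The probabilities are illustrative, and the larger gap needs a three-patient start.

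**Conclusion.** The concern holds. For one DLT in six in an Arm 2 cohort below 800 mg, the protocol both bars and directs escalation, and nothing sets an order of precedence. This is a contradictory decision rule feeding the combination MTD and RP2D in a first-in-human trial, and it must be fixed.

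The effect is confined to that one outcome. Under assumed DLT rates of 10% to 20%, the two wordings differ by about 6 to 7 points in the chance of escalating past a level from a one-patient start, and by 18 to 20 points from a three-patient start. These sizes assume independent patients and rules applied without discretion. The contradiction itself rests on the text alone.

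**What to change.** Reconcile the Section 5.5 sentence with 5.4.3, 5.6 and primary endpoint (c), so that one DLT in six leads to a single stated decision in Arm 2. If the reconciled text stops escalation in that case, also state in 3.4.2 how the MAD and MTD are then assigned. Check that Figure 4, which is captioned for Arm 1 and was not visible for this review, agrees with the result and say whether it applies to Arm 2. Which rule is right is for the sponsor and investigators to decide.

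The cost is one sentence in an amendment and at most one clause in 3.4.2. No extra patients are needed.

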3 TRIAL DESIGN

3.1 Clinical trial objectives and endpoints

3.1.1 Primary objectives and endpoints

Primary objectives	Endpoints
Part A Escalation phase	
Arm 1: To propose a recommended dose for Phase II evaluation of BI-1206 as a single agent in by:	
(a) Establishing the maximum tolerated dose (MTD) or maximum administered dose (MAD) of BI-1206 given once weekly for four weeks, via intravenous infusion in patients with relapsed or refractory B-cell malignancies in Part A only.	(a) Determining the maximal dose (up to 800 mg) of BI-1206 at which no more than one patient out of up to six patients at the same dose level experience a highly probably or probably BI-1206 related dose-limiting toxicity during induction therapy and up to one week post the fourth infusion.
(b) Assessing the safety and toxicity profile of BI-1206 as a single agent in Part A and Part B	(b) Documenting adverse events (AEs), serious adverse events (SAEs) (graded according to NCI-CTCAE Version 4.02) and laboratory parameters and determining their causality in relation to BI-1206. Causality of AEs/SAEs will be assessed by the Investigator.
Arm 2: To propose a recommended dose for Phase II evaluation of BI-1206 in combination with an anti-CD20 antibody by:	
(c) Establishing the MTD or maximum administered dose MAD of BI-1206 and an anti-CD20 antibody given once weekly for four weeks, via intravenous infusion in patients with relapsed or refractory B-cell malignancies in Part A only.	(c) Determining the maximal dose (up to 800 mg) of BI-1206 at which no more than one patient out of up to six patients at the same dose level experience a highly probably or probably BI-1206 or anti-CD20 antibody-related dose-limiting toxicity during induction therapy and up to one week post the fourth infusion.
(d) Assessing the safety and toxicity profile of BI-1206 in combination with an anti-CD20 antibody in Part A and B.	(d) Documenting AEs, SAEs (graded according to NCI-CTCAE Version 4.02) and laboratory parameters and determining their causality in relation to BI-1206 and, where appropriate, anti-CD20 antibody. Causality of AEs/SAEs will be assessed by the Investigator.
Part B Expansion phase	

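### The six-patient minimum for an MTD does not cover the routes where the MAD equals the MTD, so DLT evidence at the declared dose can be one patient in either arm

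*Combined protocol and SAP*

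**What the plan says.** **The minimum.** Section 5.6: "At least six patients will be treated at a dose below the MAD to define the MTD". This follows the case where two DLTs have fixed the MAD.

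**The other routes.** The next paragraph of Section 5.6 says "The MAD could also equal the MTD in the event that dose escalation is stopped before two DLTs are observed at a given dose level", on the expectation that higher doses would be too toxic, "or if the 800 mg dose level is reached". Sections 3.4.1 and 3.4.2 repeat both routes for the two arms. None gives a number of patients.

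**The endpoint.** Section 3.1.1 asks for "no more than one patient out of up to six patients at the same dose level" with a related DLT. Six is a ceiling here, not a floor.

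**Expansion.** Section 5.6: "Cohorts may be expanded to six patients as described in Sections 5.4.1 and 5.4.2". From Cohort 2 onwards, however, Section 5.4.2 expands to at least three, after a clinically relevant related toxicity of Grade 2 or higher. Expansion to six is in Section 5.4.3 and needs a DLT.

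**Cohort size.**
- Table 1 (Section 5.4), titled "Proposed single agent dose escalation schedule (subject to revision based upon emerging safety data; Part A, Arm 1" in its scope, gives 1 to 3 patients at 100, 200 and 400 mg and 3 + 3 at 800 mg. Footnote b says the sizes assume that no DLT occurs.
- Section 5.4.2: "From Cohort 2 onwards, all cohorts will include a minimum of one patient". It makes no exception for 800 mg.
- Section 5.5, for Arm 2: "Combination cohorts will also be a minimum of one patient". Arm 2 takes dose levels and maximum increments from Table 1, but not cohort sizes.

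**The concern.** Finding the MTD or MAD is a primary objective in both Part A arms. The plan sets its own standard for an MTD, six patients, but applies it on only one of the routes by which an MTD can be declared. On the other routes the same label can be attached to a dose at which one patient has completed the DLT window. A reader of the report could not tell from the label whether it stands for one DLT-free patient or six.

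The declared MTD or MAD then feeds the choice of RP2D, at which up to 25 patients per arm are treated in Part B. Section 3.3 applies the DLT definition to Part A only.

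**Working it through.** **1. The plan's own figure.** The plan states no target DLT rate, error rate or precision for the MTD rule. The only planned figure that bears on cohort size at 800 mg is the total of up to 81 evaluable patients (Section 1).
- Table 1 upper sizes with six at 800 mg: Arm 1, 1 + 3 + 3 + 3 + 6 = 16. Arm 2, assuming the 100 to 800 mg levels, 3 + 3 + 3 + 6 = 15. Part B, 25 + 25 = 50. Total 81, which matches.
- With three at 800 mg: 13 + 12 + 50 = 75, which does not match.
- With the synopsis's own limits: 19 + 15 + 50 = 84, which does not match.
- 19 + 12 + 50 = 81 also matches, but contradicts the stated 15 for Arm 2.

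The total is therefore consistent with six at 800 mg in each arm, but does not prove it.

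**2. Smallest DLT-free cohort the text allows when the MAD equals the MTD.**

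| Route | Source | Patients |
|---|---|---|
| Arm 1, stopped at 100 to 400 mg | Table 1 and 5.4.2 | 1 |
| Arm 1, 800 mg | 5.4.2 | 1 |
| Arm 1, 800 mg | Table 1, 3 + 3 read as a conventional 3+3 | 3 |
| Arm 1, 800 mg | Table 1, 3 + 3 read with footnote b | 6 |
| Arm 2, any level | 5.5 | 1 |

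**3. Precision at the declared dose.** With no DLT in n patients, the exact one-sided 95% upper limit is 1 − 0.05^(1/n):
- 0/1: 95.0%
- 0/3: 63.2%
- 0/6: 39.3%

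The six-patient rule also accepts 1/6. Its limit solves (1−p)^6 + 6p(1−p)^5 = 0.05, giving 58.2%.

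**4. Probability that a dose is accepted, comparing whole rules.** Let p be the true DLT rate.
- One patient, expanded to six after a DLT: (1−p) + p(1−p)^5.
- 3+3, expanded to six after one DLT: (1−p)^3 + 3p(1−p)^2 × (1−p)^3.
- Six always treated, at most one DLT: (1−p)^6 + 6p(1−p)^5.

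| Assumed p | One-patient start | 3+3 | Always six |
|---|---|---|---|
| 20% | 0.866 | 0.709 | 0.655 |
| 33% (1/3) | 0.667 + 0.044 = 0.711 | 0.296 + 0.132 = 0.428 | 0.088 + 0.263 = 0.351 |
| 50% | 0.500 + 0.016 = 0.516 | 0.125 + 0.047 = 0.172 | 0.016 + 0.094 = 0.109 |

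The one-patient column is an upper bound, because it ignores expansion to at least three after a clinically relevant related toxicity of Grade 2 or higher.

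**The case against.** **A minimum of one is a floor.** A 3+3 cohort satisfies Section 5.4.2, and Table 1 can be read as the more specific rule at 800 mg. Cohort size is also an explicit item for the dose decision meeting (Section 5.3.2). Figure 4, to which Section 5.4.2 refers, is not shown in the available text and may carry a number. All this stands, but it leaves the size to discretion. Table 1 is itself open to revision and does not reach Arm 2.

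**The one-patient route is narrow.** Clinically relevant toxicity or a DLT enlarges the cohort, and after one DLT in six the arm continues with cohorts of at least three (Section 5.4.3). An early stop needs an expectation of excess toxicity higher up, which a single uneventful patient would hardly supply. It could, however, come from the other arm or another trial, both of which the plan lets the meeting consider.

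**Stronger readings that the documents do not support:**
- *Three patients in Arm 1, one in Arm 2.* One is possible in both arms. That 0/3 suffices at 800 mg in Arm 1 is only one reading, since footnote b and the total of 81 fit six.
- *Table 1 contradicts Section 5.5.* Table 1 covers Arm 1 only. For Arm 2 there is a gap, not a conflict.
- *The RP2D rests on one patient.* Section 5.6 bases it on all Part A PK/PD and toxicity data from both arms, plus other BI-1206 trials. Only the DLT evidence at the declared dose can be that small.
- *Three patients are far weaker than six.* Comparing rules as operated, 3+3 is somewhat more permissive than always six. The large difference is at one patient.
- *Part B has no safety control.* Section 5.9 has dose-modification criteria reviewed from Part A data, Section 9.8 has regular safety review, and Section 12 ends recruitment for toxicity.

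**Conclusion.** The concern holds for the DLT evidence behind a declared MTD. The six-patient minimum in Section 5.6 does not extend to the routes where the MAD equals the MTD, and the text permits one DLT-evaluable patient in either arm. After 0/1 the data exclude only DLT rates above 95%, against 39% after 0/6 and 58% after 1/6. At an assumed true rate of 33%, acceptance is up to 71% from a one-patient start, against 35% when six are always treated; at 50% it is up to 52% against 11%.

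These probabilities rest on an assumed range of true rates, since the plan states no target, and on independent patients with a common DLT rate. The meaning of 3 + 3 at 800 mg is unresolved and could narrow the problem in Arm 1 at that level. It would not do so in Arm 2, or where Arm 1 stops lower. The matter should be settled before an MTD is declared in either arm.

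**What to change.** Reconcile Sections 3.4.1, 3.4.2, 5.4 (Table 1 and footnotes), 5.4.2, 5.4.3, 5.5 and 5.6, together with Figure 4, as follows:

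1. Apply the six-patient minimum already in Section 5.6, counted in patients evaluable under Sections 3.5.3 and 3.5.4, to every route by which an MTD is declared, in each arm.
2. State what 3 + 3 means at 800 mg in Arm 1 and whether it applies in Arm 2.
3. If fewer than six are treated at the final dose, report it as a MAD with its exact DLT-rate interval, and not as an MTD.
4. Correct the cross-reference in Section 5.6, so that expansion to six from Cohort 2 onwards points to Section 5.4.3.

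This point does not call for a DLT stop in Part B, which enrols a CD32b-selected population.

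**Cost.** At most 6 − 1 = 5 more Part A patients per arm at the declared dose, and a short delay while they complete the DLT window. Six at 800 mg in each arm fits the planned 81 (16 + 15 + 50, assuming Arm 2 uses the 100 to 800 mg levels). An arm stopped at 400 mg with six there uses fewer: 1 + 3 + 3 + 6 = 13 in Arm 1 and 3 + 3 + 6 = 12 in Arm 2. The synopsis figures, which add to 84, should be corrected at the same time.
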